PROTOCOL SUMMARY

Evaluating Alternative Medical Therapies in Primary Hyperparathyroidism

NCT02525796

2/2/2021

**AIM:** To conduct a double-blinded, placebo-controlled, randomized intervention study to investigate whether mineralocorticoid receptor (MR) antagonism, alone or in combination with cinacalcet, is an effective therapy for primary hyperparathyroidism (P-HPTH).

- Hypothesis: The aim will test the hypothesis that MR antagonism is a mechanism to lower parathyroid hormone (PTH) in primary hyperparathyroidism (P-HPTH).
- Study Design: Sixty subjects with P-HPTH will be enrolled to randomly receive eplerenone (a potassium-sparing diuretic that directly blocks the MR), amiloride (a potassium-sparing diuretic that *does not* directly block the MR), or placebo for 4 weeks +/- 3 days. Thereafter, *all* subjects will receive cinacalcet therapy (a calcimimetic that lowers PTH) *in addition* to their randomized intervention for an additional 2 weeks +/- 3 days.
- Anticipated Results: In this novel proof-of-concept study, eplerenone therapy will lower PTH, serum calcium, and markers of bone resorption in P-HPTH, when compared to placebo. The PTH response to amiloride will resemble that of placebo, suggesting that the eplerenone mediated reductions in PTH are specific to interactions with the MR. Combination therapy with eplerenone + cinacalcet will result in additive or synergistic reductions in PTH, when compared to placebo + cinacalcet or placebo + amiloride.
- Implications: MR antagonism (alone or in combination with cinacalcet) may be a mechanism to lower PTH and calcium in P-HPTH, thereby identifying a new potential option in the limited medical therapies for P-HPTH.

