## **SAMPLE SIZE:**

A sample size of up to 60 total subjects has been chosen using very conservative calculations stemming from our preliminary data (see Detailed Protocol). Therefore, at most there will be 20 subjects per study arm; however, our sample size calculations suggest that we are likely to be adequately powered with a significantly smaller sample size as well. These sample size calculations to achieve sufficient power to observe the primary and secondary outcomes of the study:

- **Primary Outcome:** Change in PTH levels ( $\Delta$ PTH) following randomized drug intervention (**Figure; visits A=>B**).
- **Secondary Outcomes:** Change in serum iCa and markers of bone resorption following randomized drug intervention (**Figure; visits A=>B**).
- Exploratory Outcome 1:  $\Delta$ PTH in response to amiloride therapy (**Figure; visits A=>B**)
- Exploratory Outcome 2:  $\Delta$ PTH in response to combination drug therapy with EPL+ cinacalcet (**Figure; visits A=>B**).
- Exploratory Outcome 3: Correlation of eplerenone-induced  $\Delta$ PTH with MR expression from adenomatous/ hyperplastic parathyroid glands of subjects that undergo parathyroidectomy following study completion.

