## Statistical Plan

**Analytic Plan, Sample Size and Power:** A sample size of 20 subjects per intervention arm (n=60 total) has been chosen using conservative calculations. The **primary outcome**,  $\Delta$ PTH in response to randomized drug therapy, will be analyzed using a 2-arm ANOVA analysis evaluating the difference between EPL and placebo. A 3-arm ANOVA including the amiloride arm will also be conducted. Sample size calculations are presented in **Figure** using preliminary data from the RAAS-PARC study where the  $\Delta$ PTH= -13 pg/mL was seen with RAAS inhibition in participants with P-HPTH, but also using a more conservative estimate (-9.0 pg/mL) that is 25% lower. It is expected that  $\Delta$ PTH with placebo will range from 0 to +4.57 pg/mL, and calculations have been made to anticipate that amiloride may serve as either a negative control (like placebo) or positive control (like EPL). With these conservative estimates, a sample size of 20 subjects/arm will be sufficient to demonstrate a  $\Delta$ PTH with a type I error of <0.05 and power=80%.

The **secondary outcomes**, change in calcium, will be analyzed in the same fashion as PTH. For calcium, sample size calculations are based on decreases in *total calcium* seen in the RAAS-PARC study ( $\Delta$ Ca= -0.32 mg/dL); treatment with EPL is expected to result in a much greater effect estimate. Thus, using *conservative* estimates of  $\Delta$ Ca= -0.20 to -0.32 mg/dL, a sample size of 20 subjects per intervention arm will be sufficient to achieve 80% power.

**Figure:** Sample size calculations based on  $\Delta$ PTH.

	$\Delta$ PTH	$\Delta$ PTH	$\Delta$ PTH	SD	Sample Size per Arm	
	Placebo	Amiloride	SPIRO		PWR=0.8	PWR=0.9
2-arms	0 pg/mL	-	-9.0 pg/mL	9.4	19	24
	0 pg/mL	-	-13.0 pg/mL	9.4	10	13
	0 pg/mL	0 pg/mL	-9.0 pg/mL	9.4	17	22
	0 pg/mL	0 pg/mL	-13.0 pg/mL	9.4	9	11
	0 pg/mL	-6.5 pg/mL	-13.0 pg/mL	9.4	12	15
	0 pg/mL	-9.0 pg/mL	-13.0 pg/mL	9.4	11	14
3-arms	0 pg/mL	-13.0 pg/mL	-13.0 pg/mL	9.4	9	11

**Figure:** Sample size calculation based on  $\Delta$ Ca.

	$\Delta$ Ca	$\Delta$ Ca	$\Delta$ Ca	SD	Sample Size per Arm	
	Placebo	Amiloride	SPIRO		PWR=0.8	PWR=0.9
	0 mg/dL	0 mg/dL	-0.20 mg/dL	0.21	17	22
	0 mg/dL	0 mg/dL	-0.32 mg/dL	0.21	8	10

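### The specificity argument needs amiloride to be shown similar to placebo, but the SAP plans only tests for a difference and gives no interval or margin; read as similarity, non-significance would miss the SAP's own −6.5 pg/mL amiloride scenario 43% of the time (minor, exploratory outcome)

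*Protocol*

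**What the plan says.** The Protocol Summary, under Anticipated Results, predicts that "The PTH response to amiloride will resemble that of placebo, suggesting that the eplerenone mediated reductions in PTH are specific to interactions" with the MR. Under Study Drug Interventions, amiloride is described as a second control whose purpose is to shed light on mechanism. The protocol's Sample Size section lists the change in "PTH in response to amiloride therapy" as Exploratory Outcome 1.

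The SAP's Statistical Plan says that the primary outcome "will be analyzed using a 2-arm ANOVA analysis evaluating the difference between EPL and placebo", and adds a three-arm ANOVA that includes amiloride. On sizing it says that "calculations have been made to anticipate that amiloride may serve as either a negative control (like placebo) or positive control (like EPL". The sample size is justified "with a type I error of <0.05 and power=80" per cent. The ΔPTH table has amiloride scenarios of 0, −6.5, −9.0 and −13.0 pg/mL, all with SD 9.4.

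The available text does not define what counts as resembling placebo. It specifies no amiloride–placebo or eplerenone–amiloride contrast, no confidence interval and no margin.

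**The concern.** The argument for specificity has two parts: eplerenone lowers PTH, and a comparable drug that does not directly block the MR does not. The second part is a claim of similarity. A test of equality cannot establish it, because a non-significant result may mean no effect or may mean too little information. Every row of the SAP's sizing tables concerns rejecting equality; none concerns showing that amiloride and placebo are close.

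The gap matters most for a partial amiloride effect. If amiloride lowered PTH by half as much as eplerenone, part of the eplerenone effect might not run through the MR. A trial of this size could easily return a non-significant amiloride–placebo difference all the same, and with no rule fixed in advance that result could be reported as support for MR-specificity.

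**Working it through.** **Inputs.** All are from the SAP's Statistical Plan unless noted.
- SD of ΔPTH: 9.4 pg/mL.
- 20 per arm: "A sample size of 20 subjects per intervention arm (n=60 total) has been chosen using conservative calculations". The protocol's Sample Size section makes this a ceiling ("at most there will be 20 subjects per study arm").
- Type I error 0.05. Sidedness is not stated. Two-sided is assumed, because a two-arm ANOVA F test is equivalent to a two-sided t test.
- Eplerenone effect: −13 pg/mL, or the "more conservative estimate (-9.0 pg/mL) that is 25% lower". The active column of the table is headed SPIRO; it is read here as the eplerenone arm.
- Amiloride effect: 0, −6.5, −9.0 or −13.0 pg/mL.

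**1. Reproduce the SAP's figures.** For a one-way ANOVA the noncentrality is λ = n × Σ(μᵢ − μ̄)² / SD².
- Two arms, 0 and −9.0, n = 19: λ = 19 × (4.5² + 4.5²) / 9.4² = 19 × 40.5 / 88.36 = 8.71. The smallest n per arm is 19 for 80% power and 24 for 90%, as in the SAP.
- Three arms, 0 / −6.5 / −13, n = 12: λ = 12 × (6.5² + 0 + 6.5²) / 88.36 = 11.48. The smallest n is 12 and 15, as in the SAP.
- The other ΔPTH and calcium rows also match. The sizing is therefore for rejecting equality. In the −6.5 row the whole of λ comes from the placebo and eplerenone means, since amiloride sits at the overall mean.

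**2. Chance of missing a real amiloride effect.** Two-sample t test, 38 df, noncentrality δ = (d/SD) × √(n/2) = (d/9.4) × √10.

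| True amiloride − placebo (pg/mL) | d/SD | δ | Power | Missed |
|---|---|---|---|---|
| −6.5 | 0.69 | 2.19 | 56.8% | 43% |
| −9.0 | 0.96 | 3.03 | 83.9% | 16% |
| −13.0 | 1.38 | 4.37 | 98.9% | 1% |

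For −6.5, using the pooled three-arm error (57 df) gives 42% missed, and a one-sided 5% test gives 31%.

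**3. Width of the interval.** SE = 9.4 × √(2/20) = 2.97. The 95% half-width is 2.024 × 2.97 = 6.0 pg/mL, which is 6.0/9.0 = 67% of the conservative eplerenone effect.

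**4. How often the misleading pattern arises.** Simulated normal data, 20 per arm, true means placebo 0, amiloride −6.5, eplerenone −13:
- Eplerenone significantly below placebo and amiloride not significantly different from placebo: about 42% of trials.
- The same, with eplerenone also significantly below amiloride: 31 to 32%.

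**5. What an interval rule would do.** Take 6.5 pg/mL purely as an illustrative margin.
- The lower 95% limit for amiloride minus placebo must lie above −6.5. With a half-width of 6.0, the estimate must be no lower than about −0.5.
- If amiloride is truly inert, the chance of meeting this equals the power at a 6.5 difference, about 57%.
- If the true effect is −6.5, the chance of wrongly meeting it is 2.5%.

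**The case against.** The strongest reply is that the quoted sentence is a forecast in a proof-of-concept study, not a decision rule. It says only that the result would be suggestive, and the amiloride response is exploratory. This stands, and it limits the severity.

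A reader might infer that the plan will treat p>0.05 as proof of resemblance. The documents do not say so. They give no criterion at all, and the planned ANOVA yields arm means and an error term from which an estimate and interval could be formed. The 43% is therefore conditional on that reading. What remains is that the rule is left open until the data are seen.

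A second reply is that the SAP text contemplates only the two extremes, placebo-like or eplerenone-like, and an eplerenone-like effect would rarely be missed (16% or 1%). That is correct. The weakness is confined to partial effects. The −6.5 row is a sizing scenario, not a prediction that amiloride will act this way.

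A third reply is that specificity also rests on eplerenone lowering PTH more than amiloride, an ordinary difference contrast with 84% power when amiloride is inert and eplerenone is at −9.0. This is fair. Adding that contrast reduces the misleading pattern from about 42% to 31 to 32%, but does not remove it, and the available text does not plan it.

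Finally, the protocol refers to a Detailed Protocol that was not supplied, and part of the SAP was not available. A margin may be stated there.

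**Conclusion.** The concern holds as a minor point on an exploratory outcome. The visible plan offers no analysis that could support the similarity on which the specificity argument depends. For a partial amiloride effect of the size the SAP itself tabulates, reading non-significance as resemblance would be wrong about four times in ten. This rests on SD 9.4, 20 evaluable patients per arm, a two-sided 5% test and normal data.

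Three stronger readings are not supported:
- A reader might quote a miss rate of 66% by supposing an effect of half an SD (4.7 pg/mL). No such amiloride effect appears in the documents.
- A reader might cut 20 per arm further for dropout. The protocol's Research Design section already allows up to 75 enrolled to cover non-completion. Because 20 is a ceiling, fewer is possible and would raise the miss rate, but no smaller number is given.
- A reader might infer that the main efficacy result is compromised. The primary eplerenone–placebo comparison does not depend on amiloride.

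**What to change.** In the SAP's Statistical Plan:
1. State that resemblance between amiloride and placebo will not be inferred from p>0.05.
2. Report the amiloride-minus-placebo and eplerenone-minus-amiloride changes in PTH, each with a 95% confidence interval.
3. Claim MR-specificity only if eplerenone lowers PTH more than amiloride and the amiloride–placebo interval excludes a reduction that the sponsor has stated in advance to be meaningful. Otherwise report the mechanism question as inconclusive.

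The sponsor should choose the margin in relation to the assumed eplerenone effect. The 6.5 pg/mL used above is only an illustration: it is half of 13, but 6.5/9.0 = 72% of the conservative effect, so excluding it could still leave much of a 9.0 effect unexplained by the MR. If a margin already exists in the Detailed Protocol, the SAP should cite it. The Anticipated Results wording in the Protocol Summary should be aligned.

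The cost is wording and two intervals from data already planned, with no extra patients. The drawback is that the claim becomes harder to make. With a 6.5 margin and a truly inert amiloride, the interval criterion alone is met about 57% of the time, and requiring eplerenone to beat amiloride as well can only lower that. A smaller margin would make an inconclusive result more likely still.

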## BACKGROUND AND SIGNIFICANCE

This proposal will investigate a novel endocrine relationship between the renin-angiotensin-aldosterone system (RAAS), the mineralocorticoid receptor (MR), and parathyroid hormone (PTH) that can be targeted to improve human skeletal health.

- ♦ The RAAS and skeletal health: The RAAS physiologically regulates sodium homeostasis and plays a pathophysiologic role in propagating cardiovascular disease; aldosterone (ALDO) and the mineralocorticoid receptor (MR) are the crucial mediators of these RAAS-associated effects. In this context, the use of RAAS inhibitors and MR antagonists has revolutionized the approach to cardiovascular disease. These pharmacologic therapies that inhibit the RAAS and block ALDO

have significantly advanced public health efforts to mitigate and treat hypertension, heart failure and death. However, it is clear that interrupting the RAAS has many *pleiotropic benefits beyond* cardiovascular health alone. One key example is the link between inappropriately high RAAS activity and the risk for developing skeletal diseases. Observational studies have shown that high ALDO levels in primary aldosteronism are associated with a high likelihood of developing osteoporosis and fragility fracture. Conversely, MR antagonism to block ALDO in small studies has been associated with protection from fracture. **Our published and preliminary data suggest that ALDO, via stimulation of the MR, can raise PTH levels and that blocking the MR may lower PTH levels.**

♦ **PTH and skeletal health:** PTH regulates calcium and bone homeostasis; however, persistent elevations in PTH decrease bone integrity and increase risk for fragility fractures. One common disorder of continuously elevated PTH is primary hyperparathyroidism (P-HPT). Recent trends in the U.S. suggest that the incidence of P-HPT is higher than previously believed, with >100,000 new cases annually with a rapidly rising prevalence (76 to 233 cases per 100K, from 1995-2010). Despite this alarming rise in P-HPT prevalence, its etiology remains largely unknown. Surgical parathyroidectomy is recommended when P-HPT is sufficiently advanced to induce clinically detectable end-organ pathology. Surgery can cure P-HPT, *but not in all cases*; the large variation in surgical practice patterns at low-volume centers is associated with higher rates of operative failure (>5%), complications (>2%), re-operation (>5%), and mortality (>1%). The future of consistently safe and effective parathyroid surgery is likely to involve highly specialized centers performing more resource-intensive procedures. Further, for many older patients (with high cardiovascular risk), or those with recurrent disease, non-surgical therapies may be preferred to minimize risk. *Therefore, new alternative non-surgical therapies for P-HPT are much needed.* Although cinacalcet (a calcimimetic) can lower PTH levels in P-HPT, trials have failed to show it can improve skeletal and cardiovascular endpoints. Importantly, P-HPT is a chronic disease, that is often monitored for years prior to definitive attempts at surgical therapy; during this monitoring time, medical therapies capable of lowering PTH levels could lower the risk of incident sequelae such as osteoporosis, nephrocalcinosis, and hypercalcemia. **Our data strongly support a novel modifiable interaction between ALDO, the MR, and PTH that may represent a target for medical therapies to lower PTH, and skeletal and cardiovascular disease risk, in P-HPT.**

♦ **The ALDO-MR-PTH Interaction:** We have developed strong evidence (see detailed protocol) to support a modifiable interaction that may address the aforementioned public health problems: **an endocrine relationship whereby ALDO stimulates PTH secretion via the MR expressed in parathyroid tissue.** Our published and preliminary data suggest that this relationship: **1)** May represent a novel determinant of PTH secretion and development of P-HPTH; **2)** Can be interrupted with a RAAS inhibitor or MR antagonist; **3)** and may be a modifiable target to reduce the risk of skeletal outcomes that are exacerbated by excess PTH, such as low bone mineral density and fragility fractures. This proposal will investigate the novel interplay between the RAAS and PTH using an innovative proof-of-concept clinical trial. The demonstration that MR antagonists can treat P-HPTH by lowering PTH (and calcium and bone turnover) could have significant public health implications.

## **RESEARCH DESIGN AND METHODS**

This is an interventional study where up to 60 subjects with active and untreated P-HPTH will be evenly randomized to receive eplerenone, amiloride or placebo in a double-blinded fashion. It is anticipated that up to 75 subjects will need to be enrolled to account for participant non-completion and withdrawals. After 4 weeks +/- 3 days of treatment, each study arm will receive cinacalcet in addition to their blinded experimental therapy. There are 3 main study visits as well as additional safety visits, which are described below. All visits will occur in the outpatient clinical research centers at BWH.

## **SAMPLE SIZE:**

A sample size of up to 60 total subjects has been chosen using very conservative calculations stemming from our preliminary data (see Detailed Protocol). Therefore, at most there will be 20 subjects per study arm; however, our sample size calculations suggest that we are likely to be adequately powered with a significantly smaller sample size as well. These sample size calculations to achieve sufficient power to observe the primary and secondary outcomes of the study:

- **Primary Outcome:** Change in PTH levels ( $\Delta$ PTH) following randomized drug intervention (**Figure; visits A=>B**).
- **Secondary Outcomes:** Change in serum iCa and markers of bone resorption following randomized drug intervention (**Figure; visits A=>B**).
- Exploratory Outcome 1:  $\Delta$ PTH in response to amiloride therapy (**Figure; visits A=>B**)
- Exploratory Outcome 2:  $\Delta$ PTH in response to combination drug therapy with EPL+ cinacalcet (**Figure; visits A=>B**).
- Exploratory Outcome 3: Correlation of eplerenone-induced  $\Delta$ PTH with MR expression from adenomatous/ hyperplastic parathyroid glands of subjects that undergo parathyroidectomy following study completion.

**INCLUSION CRITERIA:** The target study population is healthy individuals with **a physician diagnosis of active and untreated P-HPT**. P-HPT will be classified as: Serum calcium > upper limit of reference range (ULRR) **AND** serum PTH > ULRR; or Serum Calcium > ULRR **AND** serum PTH > 30 pg/mL; or Serum Calcium within 0.2 mg/dL of the ULRR and PTH>ULRR. Subjects with multiple endocrine neoplasia or recurrent P-HPT following parathyroidectomy will be included since their response to PTH lowering therapy does not differ when compared to sporadic forms of P-HPT. Subjects with hypertension will be included if their blood pressure is <150/90 mmHg. However, since it is known that ACE inhibitors and ARB's can influence PTH and that the combination of MR antagonists and ACEi/ARB medications can increase the risk of electrolyte disturbances, subjects on an ACEi or ARB will be asked to discontinue these medications for 2 weeks prior to study initiation and during the course of the study. We expect it to be very rare that a potential participant already be prescribed an MR antagonist (such as spironolactone or eplerenone) or an ENaC inhibitor (such as amiloride or triamterene); however, in these rare instances participants may still participate after a 2 week washout of these medications. Due to the potassium sparing effects of the possible study medications eplerenone/amiloride, subjects taking potassium supplements at the time of enrollment may also be asked to stop their potassium supplement (their potassium will be measured throughout our protocol, every 1-2 weeks, as part of our elaborate safety monitoring). For subjects undergoing a washout of an anti-hypertensive medication, during this medication washout, they will be prescribed doxazosin, an alpha-antagonist that does not interact with the RAAS or PTH, **if needed**, for BP control to 105-150/50-90 mmHg, as the PI has safely performed in multiple prior

research protocols (see details below). Once the study interventions are initiated (below), doxazosin will be lowered or stopped if target BP is maintained. Women of child-bearing age (age 18-50) must have a negative pregnancy test.

**EXCLUSION CRITERIA:** Subjects will be excluded if they have an estimated glomerular filtration rate < 60mL/min/1.73m^2, serum potassium > upper limit of reference range, age <18 or >80 years, diabetes that is not well controlled (HbA1c>8%), liver or heart failure, history of myocardial infarction or stroke, use of atypical antipsychotic medications or lithium, active chronic inflammatory conditions (such as inflammatory bowel disease, rheumatoid arthritis, sarcoidosis), initiation within 3 months of bisphosphonates or cinacalcet, need for imminent parathyroidectomy (within the next 6-8 weeks) as determined by their endocrinologist or surgeon, absolute serum calcium >13.0 mg/dL, or a positive pregnancy test on any of the study visits for women ages 18-50.

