In light of the COVID-19 pandemic, a remote screening visit procedure has been developed to minimize in-person contact if potential participants and study staff are unable to go into research facilities. This visit will be done by phone and televisit. We will schedule a time to complete the first portion of the screening visit over the phone at a time that is most convenient for the participant. The first portion of this visit will entail at-home monitoring of blood pressure. We will provide an at-home blood pressure monitor for the participant to measure blood pressure. Participants will be asked to remain seated with feet flat on the ground and to rest for 5-minutes prior to beginning these measurements. After 5-minutes, participants will be instructed to measure and record blood pressure and pulse three times, 2-minutes apart. At the time of the scheduled phone call, these blood pressure measurements and current height and weight are to be reported to us. In addition, personal medical history will be reviewed. If the participant meets the preliminary requirements of the study, a televisit will be scheduled with the study investigator/physician for further evaluation of eligibility.

Participants will then undergo a brief physical examination and confirmatory review of past medical history via televisit with the study investigator/physician. If the remote screening visit shows result consistent with inclusion criteria, and does not meet any exclusion criteria, we will inform the participant of their eligibility to come in for screening labs. This entails a blood draw and a urine pregnancy test (if applicable), to ensure there are no abnormalities that would

prevent participation. If the results of the screening labs meet the requirements of the study, we will inform participants within a few days that they are eligible to participate.

If participants are unable to physically come in to have screening labs drawn, they will be asked to inform us. Labs drawn within the last 3 months of signing the consent form that provide results required of the study may be used in place of screening labs to determine eligibility.

- **Study Visits:** Following screening, this study involves three main study visits (**Figure**).
  - **Visit A:** to establish baseline measurements.
  - **Visit B:** 4 weeks +/- 3 days later to assess study outcomes following blinded, randomized, intervention.

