  - **Visit C:** 2 weeks +/- 3 days later to assess study outcomes following cinacalcet add-on therapy. Additional safety visits are involved (black diamonds in **Figure**).

- **Study Drug Interventions:** Enrolled subjects will undergo detailed measurements of outcome variables (see detailed outcome variables below) to establish a baseline (**Figure, visit A**). All study visits will be conducted in the morning, following at least 1 hour of monitored supine rest in the Clinical Research Center. Following study visit A, subjects will be randomized to the blinded study drug by the BWH Research Pharmacies. The initial dose of the blinded study drug will be dictated by the subject's blood pressure and the PI's clinical judgment as it relates to reasonable safety. Subjects with blood pressures near the lower range of our safety margin of 105/50 mmHg will receive the lowest dose, and subjects with higher blood pressures (or known hypertension) will receive a higher dose. The initial doses will range from: eplerenone (EPL) 12.5 mg/d to 25 mg/BID, amiloride 1.25 mg/d to 2.5 mg/BID, or placebo. The EPL arm represents the active intervention: a direct MR antagonist. The placebo arm represents a negative control. Since EPL is expected to influence more than just PTH (EPL will also decrease blood pressure and urinary excretion of potassium and calcium) when compared to placebo, the amiloride intervention represents a *second control* to provide insights into the *mechanism* by which EPL may influence PTH. Like EPL, amiloride is a potassium-sparing diuretic, with mild anti-hypertensive and hypocalciuric effects, and will therefore induce similar changes in blood pressure and urinary potassium/calcium excretion. Unlike EPL, amiloride does not directly block the MR. Rather, it blocks epithelial sodium transport channels (ENaC) in the renal distal tubule (and vascular epithelium).

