## **BENEFITS**

There is no direct benefit from participating in this study. Subjects who participate will be clearly informed that they are not being treated for any specific medical condition, but rather are volunteering for a study that is evaluating a potential novel medical treatment for P-HPT. That being said, all participating subjects will in fact receive 2 weeks +/- 3 days of cinacalcet therapy, which is a proven and safe medical treatment to lower PTH and calcium in P-HPT. Therefore, subjects will be informed that they may receive some transient benefit in their P-HPT for 2 weeks +/- 3 days in this study, but the main objective of the study is not to be a "treatment study."

To society, if our study aims were proven correct, the results would provide a novel medical therapy for primary hyperparathyroidism with new molecular insights into disease etiology. Because P-HPT is such a common epidemiologic occurrence, evidence of a therapy to reduce PTH levels would be beneficial to society as a whole.

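### Exploratory Outcome 2 (PTH change on eplerenone + cinacalcet) is tagged visits A=>B, before any planned cinacalcet; the interval should end at visit C

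*Protocol*

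**What the plan says.** **Outcome list (Protocol, Sample Size).** Exploratory Outcome 2 is the change in "PTH in response to combination drug therapy with EPL+ cinacalcet (Figure; visits A=>B". The primary, secondary and first exploratory outcomes carry the same A=>B tag. Exploratory Outcome 3 has no visit tag. No listed outcome is tagged to visit C.

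**Timing of cinacalcet.** Research Design and Methods says that, after 4 weeks +/- 3 days of treatment, "each study arm will receive cinacalcet in addition to their blinded experimental therapy". Study Drug Interventions, under Study Procedures, likewise starts open-label cinacalcet following visit B. The Benefits section gives the total exposure: "all participating subjects will in fact receive 2 weeks +/- 3 days of cinacalcet therapy".

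**Purpose of each visit (Protocol, Study Procedures).** Visit A establishes the baseline. Visit B is "4 weeks +/- 3 days later to assess study outcomes following blinded, randomized, intervention". Visit C is "2 weeks +/- 3 days later to assess study outcomes following cinacalcet add-on therapy".

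**Comparators for the combination.** Anticipated Results, in the Protocol Summary, expects larger PTH reductions with EPL + cinacalcet "when compared to placebo + cinacalcet or placebo + amiloride". Study Drug Interventions names placebo + cinacalcet only. The arms are set in Research Design and Methods: "subjects with active and untreated P-HPTH will be evenly randomized to receive eplerenone, amiloride or placebo".

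**The concern.** An outcome meant to capture combination therapy is defined over a period in which the second drug has not been started. An analyst who follows the tag would report the 4-week EPL-only change under the combination heading.

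The aim covers mineralocorticoid receptor antagonism both alone and combined with cinacalcet, and this is the only outcome in the list that concerns the cinacalcet phase. So the tag matters more than a slip in background text, although the outcome is exploratory.

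The comparator wording raises a smaller question. If placebo + amiloride is not a regimen in the trial, the reader cannot tell from the Protocol Summary whether the amiloride arm is meant to serve as a comparator in the combination phase.

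**Working it through.** **1. The plan's own figures.** The plan gives no sample size or power for Exploratory Outcome 2. The SAP's tables size the PTH and calcium changes after randomized drug. Every row reproduces exactly with a two-sided 5% two-sample t-test (2 arms) or a one-way ANOVA F-test (3 arms). For example, a 2-arm difference of -9.0 pg/mL with SD 9.4 needs 19 per arm for 80% power and 24 for 90%. None of these figures depends on the interval chosen for Exploratory Outcome 2.

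**2. Cinacalcet exposure on the visit schedule.** Inputs: visit B at 4 weeks +/- 3 days; cinacalcet from visit B; visit C 2 weeks +/- 3 days later (Study Procedures).

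- Visit A = day 0.
- Visit B = 28 +/- 3, so day 25 to 31.
- Visit C = visit B + 14 +/- 3. Earliest 25 + 11 = day 36; latest 31 + 17 = day 48.

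| Interval | Length (days) | Planned cinacalcet days |
|---|---|---|
| A=>B (as tagged) | 25 to 31 | 0 |
| B=>C | 11 to 17 | 11 to 17 |
| A=>C | 36 to 48 | 11 to 17 |

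**3. What the tagged outcome measures.** In the EPL arm, the A=>B change in PTH is the primary-outcome change. Its contrast with placebo is the primary contrast. On the SAP's planning values for the active arm (-9 and -13 pg/mL), that is:

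- placebo change 0: -9 - 0 = -9 and -13 - 0 = -13;
- placebo change +4.57, the upper end of the SAP's range: -9 - 4.57 = -13.57 and -13 - 4.57 = -17.57.

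These values illustrate the duplication. They do not estimate a combination effect.

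**4. What an interval ending at C would measure.** Within each subject, (C - A) = (B - A) + (C - B). A=>C is the change over the whole regimen. B=>C is the increment after cinacalcet is added. Both contain all the planned cinacalcet, but they answer different questions.

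**5. Comparators.** Three arms, each then given cinacalcet, yield three combination-phase regimens: EPL + cinacalcet, amiloride + cinacalcet, and placebo + cinacalcet. Placebo + amiloride is not among them, and no double-dummy dosing is described that would create it.

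**The case against.** The strongest reply is that this is a copied label that nobody would follow. All four visit tags in the list read A=>B, which suggests copying. Study Procedures says plainly that visit C assesses the add-on, and Study Drug Interventions states the combination comparison. This stands in part: the intended end visit can be recovered, which lowers the risk of misreporting. But the outcome list is where the outcome is defined, and that definition conflicts with the rest of the Protocol.

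A second reply concerns exposure. The exclusion criteria bar only recent initiation of cinacalcet (within 3 months), so longer-standing use is not expressly addressed there. Participants are, however, described as untreated at entry, and prior use would not be the protocol's combination therapy. The claim is therefore limited to planned cinacalcet.

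A reader might infer more than the documents support:

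- *That the start visit is wholly undefined.* Visit A is the only baseline that the text names, and comparing EPL + cinacalcet with placebo + cinacalcet as regimens fits A=>C. B=>C is not excluded, but it is not the natural reading.
- *That a zero EPL-placebo difference over B=>C arises only with exact additivity, a stable EPL effect and similar cinacalcet dosing.* Those conditions are sufficient, not necessary, because departures can cancel. For instance, an assumed further 20% EPL effect on -9 pg/mL is 0.2 x -9 = -1.8, and a sub-additivity of +1.8 pg/mL returns the difference to 0. The documents give no figure for drift in the EPL effect after visit B, in either direction, so no size can be put on it.
- *That the add-on phase cannot answer its question.* The design is coherent and the data are collected; only the label is wrong.
- *That no source specifies the interval.* The visit figure, the Detailed Protocol and part of the SAP were not available, so no absence from them is claimed.

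**Conclusion.** The A=>B tag on Exploratory Outcome 2 is wrong as written and should be corrected. It covers 0 of the planned 11 to 17 cinacalcet days and turns the combination outcome into a second report of the EPL-arm primary change. This rests only on the Protocol's visit schedule and its stated start of cinacalcet, with no prior cinacalcet counted as combination therapy.

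The placebo + amiloride comparator is a secondary wording error. It sits in a narrative of expected results, not in an analysis specification. Amiloride + cinacalcet may have been meant, but the documents do not say so.

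The consequence is limited to an exploratory outcome. The primary and secondary outcomes and their A=>B interval, the sample size, the power and the data collection all stand.

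**What to change.** 1. In the Sample Size outcome list, change the interval for Exploratory Outcome 2 so that it ends at visit C. A=>C is the reading that fits the text. If the sponsor intends the increment from adding cinacalcet, label it B=>C. Settle this before unblinding.
2. In Anticipated Results, correct or delete placebo + amiloride, so that the comparators agree with Research Design and Methods and Study Drug Interventions.

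Stating a scale for judging additivity and tabulating cinacalcet dose by arm are optional for an exploratory outcome.

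The cost is a few words in two places. Outcome assessment already has PTH measured at A, B and C, so no visits, samples or subjects are added.
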